9.3 Discussion of Study Design

The primary study objective is to estimate antihypertensive effect of Edarbi® therapy on blood pressure in patients with overweight or obesity in routine clinical practice of HTN treatment in the Russian Federation. So the non-interventional study design was chosen as it helps to obtain data in routine clinical practice.

Non-interventional principles defined in Directive 2001/20/EC [5] permits to estimate “real life” conditions. Besides non-interventional studies help to analyze big sample sizes without special selection and screening within routine clinical practice. Thus, non-interventional design allows attaining the objective of the study.

Non-interventional study design has number of limitations. It doesn't suppose randomization or blinding, so no control group will be used. Other limitations of this study are the absence of control arm and comparator, less well defined population, compared with controlled clinical trials. But this limitation is not critical as there are direct comparisons of Edarbi® with commonly used angiotensin-converting-enzyme (ACE) inhibitors (ramipril) and ARB (valsartan, candesartan and olmesartan). Besides comparators are not used in the study due to the defined in the protocol study objectives and outcomes.

The population that is planned to include in the study supposed to be heterogeneous in terms of clinical characteristics. It is planned to avoid this bias by subgroup analysis, including patients with overweight obesity, metabolic syndrome and diabetes mellitus.

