9.4.5 Discontinuation/withdrawal of patients from the study

9.4.5.1. Criteria for Discontinuation or Withdrawal of a patient

Patients may be discontinued from study or study drug at any time, at the discretion of the investigator. Specific reasons for discontinuing a patient from the study are:

1. Voluntary withdrawal of informed consent in patient's request or at the request of patient's legally acceptable representative.

The patient (or patient's legally acceptable representative) wishes to withdraw from the study. The reason for withdrawal, if provided, should be recorded in the CRF. Note: All attempts should be made to determine the underlying reason for the withdrawal and, where possible, the primary underlying reason should be recorded (ie, withdrawal due to an AE or lack of efficacy should not be recorded in the "voluntary withdrawal" category).

2. Development of exclusion criteria or other safety reasons (not a AE or SAE) during the study.
3. Adverse Events (AE)/ Serious Adverse Events (SAE), including Patient's death

The patient has experienced an AE or SAE that requires early termination because patient is unwilling to continue because of the AE or SAE or continuation of patients' visit to the clinic is impossible or any other occurrence which can be happened.

4. Protocol deviations, incorrect enrolment of the patient. The investigator and the sponsor will decide whether there is a deviation from the protocol.
5. Lost for observation within the framework of the study. The patient did not return to the clinic and attempts to contact the patient were unsuccessful.
6. Study termination. Sponsor decision or regulatory authorities' requirement about cessation of the study.
7. Pregnancy. The patient is found to be pregnant.

Note: If the patient is found to be pregnant, the patient must be withdrawn immediately.

8. Other (specify)

If the patient is lost for observation within the framework of the study that is, it is impossible to conduct the final visit; the investigator must do its best to get in touch with the patients for getting full information and clarifying the reasons of the loss of contact. Premature end of HTN treatment by Edarbi® automatically means end of data collection.

Details for the premature termination of the study/sites as a whole are provided in section 9.6 (Premature termination or Suspension of Study or Investigational Site).

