9.4.5.2. Procedures for Discontinuation or Withdrawal of a patient

There are no special procedures of discontinuation of patients. The investigator may terminate a patient's study participation at any time during the study when the patient meets the study termination criteria described above in Section 9.4.4.1. In addition, patient/legal representative may discontinue participation in the study without giving a reason at any time during the study.

In all cases, the reason for withdrawal must be recorded in the CRF and in the patient's medical records. The patients who prematurely withdrew from the study are not replaced with new ones, and their data will be included into the final analysis. In case if investigator loses contact with the patient during the study observation, the investigator may contact with the patient directly or through the other health care professionals who observe this patient in routine practice. In that case part of CRF "End of observation" can be filled in basing on data received via e-mails/calls.

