10.5. Data collected on the End of observation

The end of observation in this study should be documented when:

- Voluntary withdrawal of informed consent in patient’s request or at the request of patient’s legally acceptable representative;
- Development of exclusion criteria or other safety reasons (not a AE or SAE) during the study;
- Adverse Events (AE)/ Serious Adverse Events (SAE) that requires early termination because patient is unwilling to continue because of the AE or SAE or continuation of patients’ visit to the clinic is impossible or any other occurrence which can be happened;
- Lost for observation within the framework of the study. The patient did not return to the clinic and attempts to contact the patient were unsuccessful;
- Patient’s death;
- Study termination. Sponsor decision or regulatory authorities’ requirement about cessation of the study;
- Pregnancy;
- Premature end of HTN treatment by Edarbi®,
- End of HTN treatment by Edarbi®,

In case if one of described above events become, investigator should fill in the last appropriate Observational visit Form and the “End of observation” Form.

The following data on the CRF titled “End of Observation” should be documented:

- Diagnose of HTN and cardiovascular diseases (changes in comparison with Baseline visit):
 - HTN target organ damage,
 - risk factors of cardiovascular diseases,
 - cardiovascular diseases.
- HNT treatment:
 - Date of the last Edarbi® intake or prolongation of Edarbi® treatment,
 - Reason(s) for discontinuation of Edarbi® treatment,
 - planned HTN treatment (if applicable) (INN, trade name, dosage regimen (single and total daily dose),
 - assessment of Edarbi® treatment by investigator (very satisfied, satisfied, neutral, unsatisfied, very unsatisfied),
 - assessment of HTN treatment by investigator (very satisfied, satisfied, neutral, unsatisfied, very unsatisfied).
- Reason(s) for discontinuation of observation

For patients who will discontinue observation in this study for any reason but continue treatment with Edarbi®, the investigator needs to report that therapy with Edarbi® will be continued on the appropriate CRF entitled “End of Observation”.

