12.3.2. Data privacy

The sponsor and responsible CRO affirm and uphold the principle of the patient's right to protection against invasion of privacy. The personal data of the NIS participants will be kept and processed with observance of the provisions of the RF federal law No. 152 "On personal data". Throughout this study, a patient's source data will only be linked to the study database or documentation via a unique identification number (for details, please, see Sections 8.5, 8.6., 8.7., 8.9).

If the written informed consent of a patient is known not to be available in spite of it being required, data for this patient is not entered into or is deleted from the database.

If a patient is included in the study in spite of being treated off-label (not according to the local SmPC), data is kept in the database and analysed separately and as part of the overall analyses as described in the Statistical Analysis Plan.

The patients will be identified in the database only by patient identification code (for details, please, see the section 8.7)

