13.1 Patient Population

Due to observational nature of this study patients will not be excluded from analysis based on their performance and/or data availability. All obtained data will be summarised after procedures of data cleaning and verification. All planned analyses (including descriptive analyses and study listings) will be performed for Full Analysis Set of data.

The following patient's populations will be included into statistical analysis:

- *Safety population*: Patients who have taken at least one dose of Edarbi® after enrolling in the study (Baseline visit)
- *All Patients Enrolled population*.

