9. EFFICACY ANALYSES

The primary, secondary, and exploratory efficacy analysis will be performed in two sets of data:

- 1) Full Analysis Set (defined as enrolled subjects who tookat least one dose of study drug)
- Per protocol analysis set (defined as subjects who took at least one dose of study drug and having all inclusion and no exclusion criteria)

For performing interim analysis data of first 470 enrolled patients will be used for the efficacy analyses listed in this section. For the interim efficacy analyses applicable methodology listed in this section is planned to be used. The interim analysis will be performed on the base of full analysis set.

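### Protocol 9.4.5.1 item 4 lets observation end for a protocol deviation or incorrect enrolment, so Month 6 blood pressure is lost where it could still be recorded

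*Protocol*

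**What the plan says.** Item 4 of Protocol 9.4.5.1 reads: "Protocol deviations, incorrect enrolment of the patient. The investigator and the sponsor will decide whether there is a deviation from the protocol". The section opens with a general permission: "Patients may be discontinued from study or study drug at any time, at the discretion of the investigator". It sets no deadline for the item 4 judgement and does not say what counts as a deviation. Protocol 9.3 says of the design: "It doesn't suppose randomization or blinding, so no control group will be used".

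Section 10.5 introduces its own list with "The end of observation in this study should be documented when" and asks for the last visit form and the End of Observation form when a listed event occurs. Protocol deviation and incorrect enrolment are not on that list.

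On analysis, the plan leans towards keeping patients:
- Protocol 13.1: "patients will not be excluded from analysis based on their performance and/or data availability".
- Protocol 9.4.5.2: "The patients who prematurely withdrew from the study are not replaced with new ones, and their data will be included into the final analysis".
- Protocol 12.3.2, on patients treated off-label: "data is kept in the database and analysed separately and as part of the overall analyses".
- SAP 9: the Full Analysis Set (FAS) is every enrolled patient with at least one dose. The per-protocol set adds only the condition "having all inclusion and no exclusion criteria".

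The primary outcome is the change in clinic SBP from baseline to Visit 4 (SAP 9.1). SAP 5 assumes missing outcomes are missing at random and does not impute them in the primary analysis.

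**The concern.** Being in the FAS and having a Month 6 reading are different things. The plan secures the first for a patient stopped under item 4, but not the second. Once observation ends, the Visit 4 reading is not collected, and no later choice of analysis set can bring it back.

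The loss is avoidable in some of these patients. Section 10.5 itself foresees people who leave observation but continue Edarbi, and their blood pressure may well still be measured in routine care. Recording such a reading adds no procedure and does not commit the analyst to using it in any particular set.

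The loss is also discretionary. The investigator and sponsor judge whether a deviation exists, at any time after enrolment and in an unblinded study. Protocol 9.4.4 relies on consecutive enrolment, with no eligible patient skipped, to limit selection bias. A loosely defined exit after enrolment weakens that protection.

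**Working it through.** **1. The plan's own precision figure.** Inputs from Protocol 13.4: SD 17.79, correlation 0.4375, two-sided alpha 0.05, half-width 1 mm Hg, probability 0.9 (conditional).
- SD of the paired difference = 17.79 × √(2 × (1 − 0.4375)) = 18.869.
- The smallest n for which the half-width t × s/√n is at most 1 with probability 0.9, given that the interval covers the true mean, is 1437 (probability 0.903).
- Enrolment = 1437 / (1 − 0.25) = 1916.

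Both figures reproduce. This point does not dispute them.

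**2. What a patient stopped under item 4 still contributes.** SAP 5 sets the windows at days 2–45 (Month 1), 46–135 (Month 3) and 136 onward (Month 6). For a patient stopped before day 136:

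| Provision | Effect |
|---|---|
| FAS membership (SAP 9) | Kept |
| Earlier data included (Protocol 9.4.5.2) | Kept, but no Visit 4 value |
| Last BP gathered on early exit (Protocol 13.2.4) | Falls in the Month 1 or Month 3 window |
| MMRM (SAP 9.1) | Earlier visits used |
| LOCF, worst-case and regression imputation (SAP 5) | Sensitivity only, if more than 1% of outcomes are missing |
| Primary change to Visit 4, not imputed (SAP 5, 9.1) | Nothing |
| Month 6 responder and target rates (SAP 9.2) | Nothing, unless imputed in a sensitivity analysis |

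Because 10.5 omits this reason, its instruction to complete the last visit form is not explicitly triggered. Protocol 9.4.5.2 does require the reason for withdrawal to be recorded in every case.

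**3. Which analysis set loses data.** A wrongly enrolled patient is outside the per-protocol set by definition, so the loss falls on the FAS. An eligible patient with a later deviation belongs to both sets, so both lose the value.

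**4. Size of a possible shift (illustration; q and d are assumed).** Let q be the share removed and d the difference in mean change between kept and removed patients. The full mean is (1 − q) × kept + q × removed, so kept mean minus full mean = q × d.

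| q | d = 5 mm Hg | d = 10 mm Hg |
|---|---|---|
| 1% | 0.05 | 0.10 |
| 2% | 0.10 | 0.20 |
| 5% | 0.25 | 0.50 |

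The sign depends on whether those removed were doing worse or better than those kept.

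**5. Precision, only if these exits come on top of the 25% allowance.** Pairs left = 1916 × (0.75 − extra), rounded down.
- Extra 1%: 1417 pairs, probability of half-width ≤ 1 is 0.82.
- Extra 2%: 1398 pairs, probability 0.71.
- Extra 5%: 1341 pairs, probability 0.29, expected half-width 1.01.

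If they fall inside the 25%, planned precision is unaffected.

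**The case against.** The strongest reply is that the plan already deals with early leavers. Their data are included, a last reading is gathered, the MMRM uses Visits 2 and 3, and three imputation analyses follow once more than 1% of outcomes are missing. That is fair, and it limits the damage. None of it puts a Month 6 value into the unimputed primary estimate.

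A second reply is that deleting item 4 closes little. The opening sentence of 9.4.5.1 and its Other category would still allow the same exits, perhaps under a less informative label. This stands, so the remedy needs an explicit follow-up rule as well as a deletion. The gap in 10.5 may also be editorial, since that list omits the Other category too.

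Three stronger readings are tempting, and the documents do not support them:
- **That patients are removed because of their blood pressure.** The investigator records it and is not blinded; the sponsor's view is inferred from data access and the SAP's interim analysis. But no passage ties item 4 to response, incorrect enrolment turns on entry facts, and discontinuation is permitted rather than required.
- **That item 4 flatly contradicts Protocol 13.1, 12.3.2 and SAP 9.** Those passages govern analysis, and item 4 governs observation. A patient can leave observation and remain in the FAS. They show an aim that item 4 serves badly. The direct mismatch is with 10.5.
- **That the FAS and per-protocol comparison loses its meaning because ineligible patients have no value in either set.** Ineligible patients are never in the per-protocol set. What weakens is the FAS side, and only to the extent that such patients lack Month 6 readings.

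**Conclusion.** The concern holds as a matter of avoidable, discretionary missing primary data. Item 4 allows observation to end on a judgement with no time limit or objective definition, 10.5 does not list the reason, and a patient stopped before day 136 is counted in the FAS without informing the primary estimate.

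The size cannot be known from the documents. The 0.05–0.50 mm Hg range rests on assumed removal shares and assumed differences, and the direction is open. A shift above the 1 mm Hg half-width would need much more: for example, 10% removed for this one reason with a mean change of −5, against the pooled −17.311. That gives (−17.311 + 0.10 × 5) / 0.90 = −18.68, a shift of 1.37. Ten percent would be 40% of the whole 25% dropout allowance, and nothing in the documents points to it.

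The half-width applies to the combined Russian and Kazakh sample. SAP 2.4 notes that no sample size was planned for Kazakhstan alone. The change is worth making because it is cheap and the lost readings cannot be recovered later, not because a large bias has been shown.

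**What to change.** Reconcile 9.4.5.1 with 10.5 by removing item 4 as a reason to end observation, and add a rule such as:

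*A protocol deviation or incorrect enrolment is recorded and is not by itself a reason to end data collection under any heading, including investigator discretion or Other. While the patient remains on Edarbi and valid consent stands, BP taken in routine practice is recorded to Visit 4. The patient stays in the FAS; patients failing an eligibility criterion are left out of the per-protocol set as the SAP defines it.*

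Data without valid written consent stay outside this rule. That includes patients enrolled contrary to exclusion criterion 6, who may have signed a form without being able to give valid consent. Treatment decisions remain with the physician. The SAP's per-protocol definition needs no change.

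The cost is a protocol wording change and a few more routine-visit forms. The FAS will hold Month 6 values from some ineligible patients, which the per-protocol analysis already separates. The rule does not help patients who stop Edarbi, because 9.4.5.1 ends data collection when Edarbi treatment ends early.

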9.4.5.2. Procedures for Discontinuation or Withdrawal of a patient

There are no special procedures of discontinuation of patients. The investigator may terminate a patient's study participation at any time during the study when the patient meets the study termination criteria described above in Section 9.4.4.1. In addition, patient/legal representative may discontinue participation in the study without giving a reason at any time during the study.

In all cases, the reason for withdrawal must be recorded in the CRF and in the patient's medical records. The patients who prematurely withdrew from the study are not replaced with new ones, and their data will be included into the final analysis. In case if investigator loses contact with the patient during the study observation, the investigator may contact with the patient directly or through the other health care professionals who observe this patient in routine practice. In that case part of CRF "End of observation" can be filled in basing on data received via e-mails/calls.

9.5 The study plan (plan of observation)

A physician makes the decision to prescribe Edarbi® to a patient. Afterwards the physician evaluates inclusion/exclusion criteria and offers the patient participation in the observational study.

The investigator gives the patient necessary information about the study and asks the patient to read the Patient Information Sheet and Informed Consent Form. If the patient agrees to participate in the study then the patient and the investigator sign the Inform Consent Form and the investigator includes the patient in the study.

During participation in the study patients are observed according to the local routine practice. The assignment of a particular therapeutic strategy to the patient including all diagnostic procedures is decided in accordance with Russian guidelines "Diagnostics and treatment of hypertension" (2010) and Kazakh protocol on clinical diagnosis and treatment of hypertension (2013) [6, 7] and local routine practice. The patients would take Edarbi® according to local SmPC.

[figure not shown]
Due to the non-interventional study design it's not possible to appoint exact times for the study visits, although it is expected that the period of observation will be approximately 6 months. The frequency of the visits will be assigned by each physician according to their routine practice. It is anticipated that the patients will visit their physician every 3 months and more often at the beginning until the patient achieves target blood pressure. Information for the study will be collected from 4 patients' visits to the physician:

- Visit 1 (Baseline visit): is carried out after the physician made the decision to prescribe medication and the patient signed the Informed Consent Form. Baseline visit is the visit when the patient was prescribed appropriate medication.
- Visit 2 (Observational visit): assessment of blood pressure dynamics, data collection is performed approximately one month after therapy beginning
- Visit 3 (Observational visit): assessment of blood pressure dynamics, data collection is performed approximately 3 months after therapy beginning
- Visit 4 (Final observational visit): assessment of therapy effectiveness. Data collection is performed approximately 6 months after therapy beginning

Last visit can occur later than 6 months after baseline but not more than 7 months total.

Conditions when the special form “End of observation” should be filled in earlier than patient passes 6 months are described in the Section 10.5.

Scheme 1. The observational study schematic

9.6. Premature Termination or Suspension of Study or Investigational Site

The study will be completed as planned unless appearing of situation which will require temporary suspension or early termination of the study.

The sponsor has the right to close the study with serving a preliminary written notice to investigators and hospitals. The sponsor has the right to unilaterally stop at any time enrollment of patients and / or gathering of data in the study with serving a preliminary written notice thereof on

the Investigator indicating the date of stop of enrollment. The sponsor should ensure that notification about premature termination or suspension of the study is submitted to the concerned authorities and IEC.

The investigator has the right to stop recruitment at any time with serving a preliminary written notice to the Sponsor/responsible CRO.

In case of premature closure of the site/termination of the study, all completed and also unused (including the unused pages of partially completed CRFs) CRFs and all documentation forms (except documentation that has to remain stored at site) must be returned to the Sponsor, even unused ones. Study material may be destroyed only with permission of the Sponsor.

10 Conduct

10.1. Data source

Data collection should be started only after Informed Consent Form is signed by the investigator and patient. A unique patient identification number (patient number) will be assigned to each patient at the time that informed consent is obtained; this patient number will be used throughout the study. Source data will include medical records or other sources of information (e.g. laboratory tests forms, validated copies of medical summaries given by other specialists etc.).

